9.9.1. Missing Data

It is anticipated that the degree of completeness for the study variables may vary due to unknown or undocumented data in the medical records. The number of patients with missing data for each variable will be summarized and reported. With the exception of the imputation of partial missing date values, no other imputation of missing values is anticipated; however, the impact of missing data on interpretation of findings will be acknowledged and discussed in the final study report. The SAP will further provide a detailed description of methods to deal with missing data and censoring.

9.9.2. Planned Analysis

9.9.2.1. Analysis Plan for Primary Objectives

Mortality/survival rates will be summarized and reported. Clinical, radiological, and mycological response documented in the medical record will be summarized using proportions and counts for each category. Details of radiological and mycological assessments will be reported in a descriptive manner, including the type of assessment and the assessment findings. Definitions of response will be provided in the SAP. Time to response and all-cause mortality will be analyzed using the KM method and quartiles and 95% CIs will be reported.

Descriptive statistics will be used to describe all AEs and SAEs reported during the medical record review. The safety data described will include event type, relationship to isavuconazole treatment (where known), event severity, event seriousness, action taken with isavuconazole treatment and outcome of the event. Definitions of AEs and SAEs will be described in the SAP. Time from index treatment to first AE onset will be summarized.

Key timepoints of interest for assessment of treatment effectiveness, safety and survival outcomes will be at 6 weeks, 12 weeks, and 24 weeks after initiation of index treatment. In the cases that usual care visits do not directly coincide with these timepoints, the time windows for assessment of outcomes will be defined in the SAP.

9.9.2.2. Analysis Plan for Secondary Objectives

Basic summaries of site and patient counts included in the study will be produced. Patients will be characterized by fungal disease type (invasive aspergillosis or mucormycosis) at the time of isavuconazole initiation, in terms of demographics, disease characteristics, medical history, treatment history, prognostic factors, and other factors which may be predictive of clinical outcome.

For isavuconazole treatment patterns, descriptive statistics will be used to summarize details of isavuconazole administration (eg, location, therapy duration, loading dose and frequency, and maintenance dose and frequency), modifications to index therapy, details of therapeutic drug monitoring (therapeutic drug monitoring [TDM], eg, assay type, outcome), discontinuation, switching, antibiotic use before and after index therapy, and concomitant medication.

Health care resource utilization during the post-index period will be reported at 6 weeks, 12 weeks, and 24 weeks after initiation of index therapy. HCRU will include counts and proportions of patients with inpatient visits, outpatient visits, ICU admissions and ER visits and use of mechanical ventilators. Reason for visits and duration of visits will be described. Inpatient LOS and ICU LOS will be derived using admission and discharge dates.

9.9.3. Interim Analysis

There are no planned interim analyses.

9.10. Quality Control

The development of the protocol and SAP will follow Pfizer's internal standard operating procedures (SOPs), which include detailed review rounds. Quality control of the statistical programming will follow the CRO's SOPs.

The CRO will follow SOPs and quality-control processes that address patient data security to ensure that patient data (as well as other confidential data) remain secure and intact. The EDC system has built-in edit checks and validations and supports electronically generated and manual queries.

Patient confidentiality will be strictly maintained. Access to the EDC system will be regulated via a hierarchical username and password control. Subject data will be de-identified through design of data entry fields that do not permit the entry of identifying information such as initials, date of birth, date of diagnoses/treatments/admissions, or center-assigned patient identifiers. Only trained site staff will enter data into the electronic CRFs. Patients' ages in whole years, but not date of birth, will be entered. Dates related to diagnosis, treatments, hospital admissions, discharges, etc. will be entered by the physician; the EDC system will calculate durations. Dates will not be stored by the EDC system and will not exist within the data set. No patient identifiers used by sites will be entered; rather the EDC program will automatically assign a study identifying number (ID) to each patient. The de-identified data as entered into the EDC system will be visible to the CRO and the Sponsor, but only center staff will be able to trace a study ID number to a patient identity, a necessary measure to allow center staff to respond to data queries raised by the CRO later.

9.11. Strengths and Limitations of the Research Methods

In the absence of a suitable existing database, this retrospective medical record review will allow the collection of real-world data in adult patients who received isavuconazole for the treatment of invasive aspergillosis or mucormycosis in the hospital setting. Unlike a prospective study, retrospective cohort designs are not sensitive to the Hawthorne effect (ie, alteration of behavior and/or prescribing practices as a result of being observed).

Limitations of this retrospective study design are acknowledged and will be documented within the study report:

- Data quality will be dependent on completeness and accuracy of the data abstraction and the data documentation in the medical records. Differences in how each site operates, the connections to other health care facilities within the medical record, and the extent to which specific details are documented will affect data availability across medical records. For example, it is expected that the timing of follow-up visits may vary across sites. Additionally, some data are less likely to be comprehensively documented, including reasons for treatment modification/discontinuation/switching, TDM, mycological/radiological response status at end of treatment, AEs, and reason for HCP visits/referrals. Moreover, visits that occur at a different site may not be documented within the medical record to which the site has access; thus, the data may not provide an accurate representation of the true health care burden. A rigorous data review and cleaning process will be undertaken to ensure that the data which is collected is of the highest quality for analysis.
- The study sites will be chosen based on a convenience sampling approach. That is, sites that indicated interest in study participation and that retain pertinent data within patient medical records that meet the study eligibility criteria were identified during the feasibility assessment. Therefore, by study design, the sites are unlikely to be fully representative of all sites in which cases of invasive aspergillosis or mucormycosis are managed with isavuconazole therapy. Thus, the data are unlikely to be representative of the overall usual care patterns for invasive aspergillosis or mucormycosis in Europe, and the study results should not be considered to be generalizable.
- Since invasive aspergillosis and mucormycosis are rare fungal infections, it is expected that the pool of potential patients across sites will be small and will vary by country.
- The sample size might not yield reliable estimates for rare safety outcomes. However, this study will allow assessment of whether commonly occurring safety events in clinical trials also are observed in real-world setting.
- As target patients are likely to have underlying severe diseases, we have designed this study specifically for a patient population found in a hospital setting, including the ER, ICU, or oncology, hematology and/or transplantation wards.
- Inpatients may change wards during isavuconazole treatment, which may impact the availability of follow-up data. Additionally, patients may be discharged from hospital but will continue to receive treatment with isavuconazole. It is possible that the abstracting HCP does not have access to data related to these instances.

9.12. Other Aspects

Not applicable.

10. PROTECTION OF HUMAN SUBJECTS

10.1. Patient Information

All parties will comply with all applicable laws, including laws regarding the implementation of organizational and technical measures to ensure protection of patient personal data. Such measures will include omitting patient names or other directly identifiable data in any reports, publications, or other disclosures, except where required by applicable laws.

The personal data will be stored at the study site in *encrypted electronic* form and will be *password protected* to ensure that only authorized study staff have access. No patient-identifying information will be collected for this study or transferred to Pfizer or the CRO. The study site will implement appropriate technical and organizational measures to ensure that the personal data can be recovered in the event of disaster. In the event of a potential personal data breach, the study site shall be responsible for determining whether a personal data breach has in fact occurred and, if so, providing breach notifications as required by law.

To protect the rights and freedoms of natural persons with regard to the processing of personal data, when study data are compiled for transfer to Pfizer and other authorized parties, the data will not contain patient names (none will be collected). Rather, individual cases will be indicated by a single, specific, numerical code, based on a numbering system defined by Pfizer. The study will not collect any identifiable data; in this way, such data cannot be transferred to Pfizer or other authorized parties. The investigator site will maintain a confidential list of patients who participated in the study, linking each patient's numerical code to his or her actual identity. In case of data transfer, Pfizer will maintain high standards of confidentiality and protection of patients' personal data consistent with the CSA and applicable privacy laws.

10.2. Patient Consent

As this study does not involve data subject to privacy laws according to applicable legal requirements, obtaining informed consent from patients by Pfizer is not required and exemption of informed consent will be requested to the Institutional Review Boards (IRBs) or Independent Ethics Committees (IECs). However, informed consent may be required in accordance with local country regulations. If informed consent is required, bias will be introduced into the study since the eligible patient population must be alive at the time of data collection. Where relevant, this will be fully documented in the study report.

If informed consent is required:

- The informed consent form (ICF) will be in compliance with local regulatory requirements and legal requirements. The ICF will be drafted using the Pfizer ICF template, with privacy language per country as required. Additionally, the final ICF and any subsequent amended versions during the study will be prospectively approved by both the IRB or IEC and Pfizer before use.

- Informed consent will be obtained by site study staff prior to data abstraction. The person obtaining consent will be responsible for ensuring that each participant fully understands the nature, purpose, risks, and benefits of the study. Each participating patient will be provided with a copy of his or her signed ICF.
- It will be the investigator's responsibility to ensure that each study patient, or his or her legally acceptable representative, is fully informed about the nature and objectives of the study and possible risks associated with participation. The investigator, or a person designated by the investigator, will obtain written informed consent from each patient or the patient's legally acceptable representative before any study-specific activity is performed. The investigator will retain the original of each patient's signed consent form.

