9.9. Data Analysis

This study is primarily descriptive in nature. Categorical variables will be reported as counts (n) and frequencies (%). Continuous variables will be reported using mean, standard deviation, median, minimum and maximum, interquartile range, and range. Time to event outcomes will be assessed using the KM method and will be reported as descriptive statistics (eg, median time to event) with 95% CI. Results will be presented for the overall group (both disease types) and separately for invasive aspergillosis and mucormycosis.

The statistical analysis plan (SAP) will provide a detailed description of analytic populations, analyses to be performed, and methods to deal with missing data and censoring.

Depending on the overall sample size, subgroup analyses may be conducted for main study outcomes (eg, by country, by diagnosis).

Detailed methodology for summary and statistical analyses of data collected in this study will be documented in a SAP, which will be dated, filed, and maintained by the sponsor. The SAP may modify the plans outlined in the protocol; any major modifications of primary outcome definitions or their analyses would be reflected in a protocol amendment. The SAP will define all planned analytic populations and subpopulations, including definitions of overall response and AEs of interest. The SAP will further provide a detailed description of analyses to be performed.

Any known deviations from the planned analyses, the reason for such deviations and all alternative/additional statistical analyses that may be performed as well as the final statistical analysis must be described in a revised SAP before completion of data collection.

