### 3 ANALYSIS POPULATION

The analysis population will consist of adult patients who received isavuconazole for the treatment of invasive aspergillosis or mucormycosis in the hospital setting. Patients who did not receive at least one dose of isavuconazole for treatment of invasive aspergillosis or mucormycosis within the eligibility period will not be considered for analysis.

*Patients must meet all of the following criteria to be eligible for inclusion in the analysis:*

1. *Patient must be aged  $\geq 18$  years at the time of isavuconazole initiation*
2. *Patient must have a record of a diagnosis of invasive aspergillosis or mucormycosis in their medical record at the time isavuconazole was initiated (regardless of whether this diagnosis is suspected or confirmed)*
3. *Patient must have received at least one dose of isavuconazole during the eligibility period (October 15, 2015, to June 30, 2019)*

*All analyses will be performed on the analysis population. Analyses of the primary endpoints may also be performed on up to three subgroups, which will be selected from the following list and determined based on sample size:*

- Neutropenia and non-neutropenia patients
- Patients with central nervous system infections
- Age (e.g.,  $<75$  years vs.  $\geq 75$  years)
- Patients with corticosteroid use at baseline
- Patients with influenza at baseline
- Patients with ICU admission where isavuconazole is initiated
- Patients with history of use of biologics

PFIZER CONFIDENTIAL

[figure not shown]
CT24-WI-GL03-RF03 1.0 *Non-Interventional Statistical Analysis Plan For Secondary Data Collection*  
*Study 16-Sep-2020*  
*Page 8 of 19*

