### 6.3 ANALYSIS OF CLINICAL OUTCOMES

Each clinical outcome will be analyzed using counts and frequencies at weeks 6, 12, and 24, along with other descriptive information about the clinical outcome itself.

Additionally, time-to-event analyses anchored on the index date of isavuconazole initiation will be performed using the KM method. For each clinical outcome, the time-to-event analyses will result in a KM plot with summary statistics, including survival-time quartiles and KM estimates at weeks 6, 12, and 24 with accompanying 95% CIs. All analyses will be performed for invasive aspergillosis patients, mucormycosis patients, and for the total study population. If subgroup analyses are pursued, Cox regression will be employed to derive HRs and accompanying 95% CIs.

For the death outcome, patients will be categorized as dead, alive, or unknown at each timepoint of interest, and primary cause of death will be tabulated (Appendix 1, Analysis Table 5.1). For KM analyses, a documented death will comprise the event, and patients will be censored at the date when they are last known to be alive (Appendix 1, Analysis Figure 1; Appendix 1, Analysis Table 5.2).

For the clinical response outcome, patients will be categorized as having clinical success, having clinical failure, or unknown response at each timepoint of interest will be tabulated (Appendix 1, Analysis Table 6.1). In addition, rates of reactivation of the same infection and rates of new infection will be documented overall and specific to whether these events occurred during isavuconazole treatment. For KM analyses, clinical response will comprise the event, and patients will be censored at the earliest timepoint of any of the following: loss to follow-up, end of study, or death (Appendix 1, Analysis Figure 2; Appendix 1, Analysis Table 6.2).

For radiological response, patients will be categorized as having a success, not having a response, unknown response, or not applicable (for the first assessment) at the relevant timepoints of interest (Appendix 1, Analysis Table 7.1). Additionally, radiological examination type and bodily location of the examination will be tabulated. For KM analyses, radiological response will comprise the event, and patients will be censored at the earliest timepoint of any of the following: loss to follow-up, end of study, or death (Appendix 1, Analysis Figure 3; Appendix 1, Analysis Table 7.2).

PFIZER CONFIDENTIAL

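### If any site needs patient consent, only survivors can enter there, and the SAP has no rule to keep the pooled mortality estimate from being biased low

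*Protocol*

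**What the plan says.** Protocol 10.2 says that an exemption from consent will be requested, but that "informed consent may be required in accordance with local country regulations". If that happens, "bias will be introduced into the study since the eligible patient population must be alive at the time of data collection". The stated response is "Where relevant, this will be fully documented in the study report". The same section also provides for consent from a patient's "legally acceptable representative before any study-specific activity is performed".

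Protocol 9.9 leaves the analysis rules to the SAP: "The SAP will define all planned analytic populations and subpopulations". It allows subgroup analyses, with country as an example, as an option that depends on sample size. It also says that deviations from the planned analyses "must be described in a revised SAP before completion of data collection".

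SAP 3 defines one population from age, diagnosis and at least one dose in the eligibility period, and says "All analyses will be performed on the analysis population". Its list of optional subgroups contains neither country nor consent status. SAP 6.3 says "All analyses will be performed for invasive aspergillosis patients, mucormycosis patients, and for the total study population". Deaths are counted at weeks 6, 12 and 24, and the Kaplan-Meier analysis runs from the index date. The SAP text does not mention consent and gives no exclusion, stratification, delayed-entry or sensitivity rule for it. The Appendix 1 table shells are in an attached spreadsheet and were not available to check.

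**The concern.** All-cause mortality is the first-named primary outcome, and the precision of the day-42 rate is what Protocol 9.5 uses to justify the study size. A site that can enter only living patients contributes people whose recorded mortality at every key timepoint is zero by construction. Adding them to the denominator lowers the proportions and the matching Kaplan-Meier estimates.

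Describing this in the report tells the reader that the figure is too low. It does not change the figure or its interval, and it does not give the estimate that lacks the problem. Response may be affected too, since survivors probably respond more often, but the documents give no planning response rate from which to size that.

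The protocol foresees the situation and says that bias follows. What is missing is the analysis rule. If it is left until the data are in, the choice of how to present mortality could be made with the results in view.

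**Working it through.** **1. The plan's own precision figures.** Protocol Table 1 gives 95% CI widths of 9.0, 10.0, 12.5 and 15.0 points at N = 292, 237, 152 and 106 for a rate of 19%. The Wilson half-width is z/(1 + z²/N) × √(p(1−p)/N + z²/(4N²)). With p = 0.19 and z = 1.96, the full widths are 8.98, 9.96, 12.41 and 14.83, so the table reproduces closely. For mucormycosis at 33% and n = 37 the half-width is 14.5 points, against a stated precision of 15%.

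**2. Can a patient entered under the condition have died by week 24?** The last index date is 30 June 2019 (Protocol 9.3.1.2) and the planned start of collection is 10 August 2020 (Protocol 6), a gap of 407 days. From the first possible index date, 15 October 2015, the gap is 1,761 days. Italy starts in October 2021, at least 824 days after the last index date. Week 24 is 24 × 7 = 168 days. A patient alive at collection was therefore alive at all three timepoints. The dates may change, but the shortest gap would have to shrink by more than 407 − 168 = 239 days to alter this.

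**3. Size of the bias.** The documents give neither the affected sites nor the share of their patients who would enter, so these are assumptions:
- k = 5 of the 22 sites need consent (Italy and Spain each have five in Protocol 9.2.1).
- Sites are of equal size.
- There are N₀ = 583 eligible records (Protocol 9.2.1).
- True day-42 mortality is p = 19% everywhere (the planning value in Protocol 9.5, from aspergillosis patients).
- A share s of the eligible patients at the affected sites is alive, traced and consenting.

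The share of analysed patients who are restricted is f = ks/((22 − k) + ks). The analysed number is N = N₀((22 − k) + ks)/22. Pooled mortality is p(1 − f), so the bias is p × f. For s = 50%, f = 2.5/19.5 = 0.128, N = 583 × 19.5/22 = 517, and the bias is 19 × 0.128 = 2.4 points.

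Coverage is the exact binomial probability that the pooled Wilson interval contains 19%, with deaths possible only among waiver-site patients.

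| N₀ | s | f | N | Pooled mortality | Bias (points) | Half-width (points) | Coverage of 19% |
|---|---|---|---|---|---|---|---|
| 583 | 20% | 0.056 | 477 | 17.9% | 1.1 | 3.4 | 92% |
| 583 | 30% | 0.081 | 490 | 17.5% | 1.5 | 3.4 | 86% |
| 583 | 50% | 0.128 | 517 | 16.6% | 2.4 | 3.2 | 72% |
| 200 | 20% | 0.056 | 164 | 17.9% | 1.1 | 5.9 | 94% |
| 200 | 50% | 0.128 | 177 | 16.6% | 2.4 | 5.5 | 89% |

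With no restricted sites, coverage at 583 is 95%. With two sites affected (as in France) and s = 50%, the bias is 0.9 points and coverage 92%. With six (as in Germany) and s = 50%, they are 3.0 points and 60%.

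**4. Precision of the waiver-site estimate.** Losing 5 of 22 sites leaves 583 × 17/22 ≈ 450, and the half-width at 19% goes from 3.2 to 3.6 points. At the 200-patient minimum, about 155 remain and it goes from 5.4 to 6.1 points. For mucormycosis, 37 × 17/22 ≈ 29 remain, and it goes from 14.5 to 16.2 points at 33%.

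**5. Would the selection be counted?** Protocol 9.6.1 records screening results for the inclusion and exclusion criteria. Those criteria (Protocol 9.2.2 and 9.2.3) mention neither consent nor being alive, so the described screening record need not show how many patients were lost for these reasons.

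**The case against.** The strongest reply is that nothing may happen. An exemption will be requested, Protocol 10.4 also plans a request for a non-interventional, not-human-data classification, and no passage names a country or site that needs consent. A reader might infer that the mortality estimate is already biased. The documents do not support that: with every site exempt the bias is zero.

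The bias is also disclosed. Protocol 10.2 names it and gives the mechanism. Protocol 9.11 says that the sites are a convenience sample and that results should not be generalised. The study is descriptive, and no test or decision rests on the estimate. This limits the consequence, but disclosure leaves the estimate and interval unchanged.

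The optional by-country analysis in Protocol 9.9 could separate affected patients if consent rules follow national borders. It is a partial route only: it need not be done, and country is not in the SAP list.

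Four stronger readings are tempting and should not be adopted:
- **Interval coverage collapses.** Coverage of about 40% appears only at s = 81%, with five sites affected, no deaths after day 42 and everyone traced and consenting. That is a ceiling. With five sites, the bias exceeds the half-width only if s is above about 66%.
- **Mortality might instead be biased upward**, if deaths were abstracted freely and only survivors had to consent. Protocol 10.2 describes the reverse restriction.
- **The representative wording contradicts the alive condition.** It can be read as covering living patients who lack capacity, so no conflict is established.
- **Affected sites must be removed from the primary analyses.** The documents do not require this. If five sites were lost, mucormycosis precision would move to 16.2 points, outside the stated 15%. For response, the bias cannot be sized.

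**Conclusion.** The point holds as a conditional gap. If any site enters patients under the condition in Protocol 10.2, those patients cannot have died by week 24, and the SAP as written pools them, so the primary mortality proportions and Kaplan-Meier estimates are too low. The direction follows from the protocol's own statement and dates.

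The size cannot be fixed from the documents. With five of 22 equal-sized sites, 583 records and 19% mortality, it is about 1.1 to 2.4 points for s from 20% to 50%: smaller than the half-width, but enough to take coverage from 95% to between 92% and 72%. At 200 patients the same bias matters less against a wider interval. Applying the aspergillosis rate to a two-disease population is a simplification.

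It should be fixed because the situation is foreseen and the rule is cheap to set in advance. Confidence is medium, since the trigger may never occur.

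**What to change.** 1. Record for each site whether it has a consent waiver or needs consent with the alive-at-collection restriction.
2. State in a revised SAP, before data collection is complete, that week 6, 12 and 24 mortality and its Kaplan-Meier estimates will be reported for waiver sites alone beside the all-site estimate, overall and by disease. Identify the waiver-site figure as the mortality estimate free of the survival restriction.
3. Report response by consent status in the same layout, as a descriptive sensitivity analysis with no mandatory exclusion.
4. Where local rules permit, count otherwise eligible patients who were not entered because of death, no contact or refusal.

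The cost is one site-level variable, SAP wording, extra columns in the outcome tables and a short log. Under Protocol 9.9 a protocol amendment would also be needed if the sponsor regards this as a major change to a primary analysis. The statistical price is the wider waiver-site intervals in step 4 of the working, felt most in mucormycosis. Because the all-site estimate stays in the report, no patient is dropped from it. If all sites are exempt, the two estimates coincide and nothing changes.
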